6.2. Products Application and Usage Instruction

Mode of application

a. 1-week wash-out stage: T-7d ~ T0 for all groups

A.M.: Standard cleanser + Standard moisturizer + Standard SPF

P.M.: Standard cleanser + Standard moisturizer

b. 2-week pre-treatment stage: T0 ~ T14d

【Group 1-Facial Serum group】

A.M.: Standard cleanser + Test serum + Standard moisturizer + Standard Sunscreen

P.M.: Standard cleanser + Test serum + Standard moisturizer

Group 2-Non-treatment group

A.M.: Standard cleanser + Standard moisturizer + Standard Sunscreen

P.M.: Standard cleanser + Standard moisturizer

The standard sunscreen needs to apply to face every morning 15 minutes before sun exposure and re-apply if necessary. Keep out of eyes. No any other skin care or facial make up products are used.

c. 10 days recovery stage: T15d ~ T24d for all groups

A.M.: Sterile saline solution + EGF

P.M.: Sterile saline solution

d. 2-week post-treatment stage: T25d ~ T39d

【Group 1-Facial Serum group】

A.M.: Standard cleanser + Test serum + Standard moisturizer + Standard Sunscreen

P.M.: Standard cleanser + Test serum + Standard moisturizer

Group 2-Non-treatment group

A.M.: Standard cleanser + Standard moisturizer + Standard Sunscreen

P.M.: Standard cleanser + Standard moisturizer

The standard sunscreen needs to apply to face every morning 15 minutes before sun exposure and re-apply if necessary. Keep out of eyes. No any other skin care or facial make up products are used.

7. Procedure

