7.2. Conducting the Study

Pre-screening visit at T-7d

- a. Within 24 hours before screening visit, subjects will be asked not to use any cosmetic product on test areas.
- b. On the arrival, the subject will be informed about the nature of the study and the treatment procedure and a signed and dated informed consent form will be obtained. At the same time, one Photo release form will be also signed from each subject.
- c. A subject screening number will be automatically allocated (SC0X) by CRF.
- d. Demographic data collection.
- e. Medical examination, subject's interview on his medical history and concomitant medications.
- f. Subjects wash face with usual cleanser, then pat dry with clean tissue paper at center.
- g. Acclimatization to the room condition for 30 minutes (the conditions with a well-controlled room temperature (21 ± 1 °C) and humidity ($45\%\pm5\%$).
- h. Clinical assessment by will be done by dermatologist for screening.
- i. Verification of subject eligibility: inclusion/non-inclusion criteria and on-site clinical grading by Dermatologist.
- j. The weighted wash-out products and daily log will be delivered to each subject.
- k. Adverse Events/Local Intolerance will be checked and recorded.

Evaluation visit on T0: Baseline

- a. Subjects wash face with usual cleanser, then pat dry with clean tissue paper at center.
- b. Acclimatization to the room condition for 30 minutes (the conditions with a well-controlled room temperature (21 ± 1 °C) and humidity ($45\%\pm5\%$).
- c. Verification of inclusion/non-inclusion criteria for final eligibility.
- d. Clinical Assessment will be done by dermatologist for T0.
- e. VISIA 7 will be done by trained technician for T0.
- f. OCT scan will be done by trained technician for T0.
- g. Corneometer will be done by trained technician for T0.
- h. Vapometer will be done by trained technician for T0.
- i. Cutometer will be done by trained technician for T0.
- j. pH meter will be done by trained technician for T0.

- k. LA sting test will be done by trained technician for T0.
- The wash-out (standard) products will be weighted and returned to subjects; as the same time, the weighted
 investigational products and daily log will be delivered to each subject according to the randomization
 table.
- m. Adverse Events/Local Intolerance will be checked and recorded.

T0 to T14d

a. Subjects should apply the provided wash-out products twice a day at home, in the morning and in the evening.

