Evaluation visit on T14d

- a. Subjects wash face with usual cleanser, then pat dry with clean tissue paper at center.
- b. Acclimatization to the room condition for 30 minutes (the conditions with a well-controlled room temperature (21 ± 1 °C) and humidity ($45\%\pm5\%$).
- c. Clinical Assessment will be done by dermatologist for T14d.
- d. VISIA 7 will be done by trained technician for T14d.
- e. OCT scan will be done by trained technician for T14d.
- f. Corneometer will be done by trained technician for T14d.
- g. Vapometer will be done by trained technician for T14d.
- h. Cutometer will be done by trained technician for T14d.
- i. pH meter will be done by trained technician for T14d.
- j. LA sting test will be done by trained technician for T14d.
- k. Self-assessment questionnaire will be answered by subjects for T14d.
- l. The investigational products and standard products will be weighted and returned to subjects, meanwhile, the daily log will be also checked.
- m. Adverse Events/Local Intolerance will be checked and recorded

Chemical Procedure visit and Timme evaluation on T15d

- a. Subjects wash face with usual cleanser, then pat dry with clean tissue paper at center.
- b. One questionnaire should be answered by subjects.
- c. Pre-process of xxx for procedure preparation.
- d. CO2-laser will be done by medical technologist.
- e. Clinical Assessment will be done by dermatologist for Timm post-procedure.
- f. VISIA 7 will be done by trained technician for Timm post-procedure
- g. OCT scan will be done by trained technician for Timm post-procedure
- h. Corneometer will be done by trained technician for Timm post-procedure
- i. Vapometer will be done by trained technician for Timm post-procedure
- j. Cutometer will be done by trained technician for Timm post-procedure
- k. pH meter will be done by trained technician for Timm post-procedure
- 1. Adverse Events/Local Intolerance will be checked and recorded.

Evaluation visit on T16d (1-day after self-recovery)

- a. Clinical Assessment will be done by dermatologist for T16d.
- b. VISIA 7 will be done by trained technician for T16d.
- c. OCT scan will be done by trained technician for T16d.

- d. Corneometer will be done by trained technician for T16d.
- e. Vapometer will be done by trained technician for T16d.
- f. Cutometer will be done by trained technician for T16d.
- g. pH meter will be done by trained technician for T16d.
- h. Self-assessment questionnaire will be answered by subjects for T16d.

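### The home-use line for T0 to T14d in Section 7.2 names only the wash-out products for all subjects, in conflict with Section 6.2 b and with Section 7.2's own dispensing steps

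*Protocol*

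**What the plan says.** Section 6.2 sets out product use by stage and group. The first stage is wash-out ("a. 1-week wash-out stage: T-7d ~ T0 for all groups"), with standard products only. The second is pre-treatment ("b. 2-week pre-treatment stage: T0 ~ T14d"). In that stage the Group 1 morning regimen is "A.M.: Standard cleanser + Test serum + Standard moisturizer + Standard Sunscreen", and the serum appears again in the evening. Group 2 uses the standard products without the serum.

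Section 7.2, under its T0 to T14d heading, has a single line: "Subjects should apply the provided wash-out products twice a day at home, in the morning and in the evening". It is addressed to subjects in general. The product step of the T0 visit, immediately before it, shows what the term covers: "The wash-out (standard) products will be weighted and returned to subjects". The same step treats the serum as a separate item: "investigational products and daily log will be delivered to each subject according to the randomization" table. At T14d, Section 7.2 says: "The investigational products and standard products will be weighted and returned to subjects, meanwhile, the daily log will be also checked".

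The study schedule in Section 4 shows standard and investigational products both distributed and weighed at T0 (V2), and both returned and weighed at T14d (V3). Its footnote describes continuous product application over the two-week pre-treatment period.

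**The concern.** The protocol states the T0 to T14d regimen twice, and the two statements differ for Group 1. This is a conflict between two written instructions, so it cannot be put down to detail left for another document.

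The period matters because it carries the whole pre-treatment exposure. In the recovery stage (6.2 c) both groups have the same care, so before T25d the groups differ only in serum use from T0 to T14d. Three sets of results depend on it:

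- the Group 1 versus Group 2 comparison in 8.3.2 at T14d to T25d;
- the Group 1 changes listed as pre-treatment efficacy in 8.3.1;
- the recovery items of the questionnaire in Annex 11.3, which ask whether using the product beforehand helped.

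The product is applied at home, so exposure depends on what subjects are told to apply.

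**Working it through.** The protocol states no figure on this point, so the check is mainly a comparison of passages.

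**Step 1. Instructions for T0 to T14d side by side**

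| Place | Group 1 | Group 2 |
|---|---|---|
| 6.2 b | standard products plus serum, morning and evening | standard products, morning and evening |
| 7.2, T0 to T14d line | wash-out products, twice a day | the same line, no split |
| 7.2, T0 visit | standard products handed back; investigational product delivered by randomization table | by the same table |
| 7.2, T14d visit | investigational and standard products weighed, log checked | the same line, no split |
| Schedule and footnote | both product types out at V2 and back at V3; continuous application in pre-treatment | no split shown |

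The 7.2 line agrees with 6.2 b for Group 2 and is short of the serum for Group 1. The other rows presuppose that the serum is in use from T0.

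**Step 2. Can the term include the serum?** Not within 7.2. The T0 step equates wash-out with standard products and names the investigational products separately in the same item. Section 6.2 a also ends the wash-out stage at T0, so the line uses the label of a stage that is already over.

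**Step 3. Does the line forbid the serum?** No. It contains no word of exclusion, and both groups do use standard products morning and evening in this period under 6.2 b. The line is incomplete for Group 1.

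**Step 4. Does 7.2 correct it elsewhere?** It has no home-use regimen line for T-7d to T0, T15d to T24d or T25d to T39d. The T0 to T14d line is the only one of its kind in the section, and it does not refer to 6.2.

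**Step 5. Direction and size of the effect**

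- Let D be the expected group difference at a visit if all of Group 1 use the serum, and m the share of Group 1 who do not use it.
- Assume that non-users respond on average like Group 2.
- Expected observed difference = (1 - m) x D.
- The Group 1 change in 8.3.1 is C + (1 - m) x D', where C is the change on standard products alone and D' is the serum's contribution to that change. Only the serum part is diluted.
- Section 2 requires at least 30 completers per group. With 30, one non-user gives m = 1/30 = 0.033, a loss of about 3.3% of D.
- Range: m = 0 loses nothing; m = 1 leaves no expected difference.

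The protocol gives no value for m, D or a target power, so no loss of power can be derived from it.

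**The case against.** The strongest reply is that a site working through the protocol would not be misled. Section 7.2 delivers the investigational product at T0 by randomization table, and weighs it and checks the daily log at T14d. The schedule includes a compliance check at every visit. Section 6.2 is headed as the usage instruction and is the only place with regimens by group. Because 7.2 is silent on home use in every other period, the site has to consult 6.2 anyway. The line could simply be a wash-out instruction that landed under the wrong heading; that is plausible, but the protocol does not say so.

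Much of this stands. A reader might infer that a site following 7.2 gives Group 1 no pre-treatment and that both groups then receive the same regimen. The documents do not support that: 7.2 itself puts the serum in subjects' hands, and the line does not exclude it. A reader might also want a figure for lost power, but any such figure would rest on an effect size and non-use shares that the protocol does not state.

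The reply does not remove the conflict. The protocol does not say that 6.2 takes precedence over 7.2. The dispensing and weighing steps show that 7.2 disagrees with itself. No visit falls between T0 and T14d, so weighing and log checks at T14d would reveal missed use only after the exposure period had ended.

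**Conclusion.** The conflict is real and limited. The T0 to T14d home-use line in 7.2 names only the wash-out (standard) products for all subjects. That disagrees with 6.2 b, with dispensing and weighing in 7.2 itself, and with the schedule footnote. The realistic risk is partial or inconsistent serum use in Group 1, which would pull the 8.3.2 comparison at T14d to T25d, and the serum's part of the 8.3.1 pre-treatment changes, towards no effect.

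The dilution is proportional to the share of Group 1 who do not use the serum, assuming that they respond like Group 2. The protocol offers no basis for estimating that share. This is an inconsistency of text that should be corrected; it does not show that the pre-treatment contrast is lost.

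**What to change.** The sponsor must reconcile the T0 to T14d line of Section 7.2 with Section 6.2 b and with the dispensing steps, so that one group-specific home-use instruction applies in that period. The home-use instructions for the other periods should be made consistent between 6.2 and 7.2 in the same pass. Which text governs is for the sponsor and investigator to settle.

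The cost is a wording amendment under Section 9.1, with ethics committee review as Section 10 requires for significant changes. Visits, measurements and sample size stay as they are. If subjects have already passed T14d, the product weights and daily logs should be used to report what Group 1 actually applied.

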5.2. Lactic Acid Test (N=60)

The lactic acid test is widely accepted as a marker of skin sensitivity and employed for the selection of subjects experiencing invisible sensory irritation. A self-assessment questionnaire (Annex 11.4) of the intensity of symptoms (stinging, itchiness, burning and other) will be answered by subject at 30 seconds, 2.5 minutes, 5 minutes after lactic application. The variation of score between 10% concentration of lactic and distilled water will be calculated and defined to the sensitive level. This process will be done at T0 (baseline), T14d (after pre-treatment), T25d (10-day after self-recovery and product treatment start), T39d (14-day after product treatment)

Score 0: Not at all

Score 1: Slight

- Score 2: Moderate

- Score 3: Severe

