- i. Adverse Events/Local Intolerance will be checked and recorded.

Evaluation visit on T18d (3-day after self-recovery)

- a. Clinical Assessment will be done by dermatologist for T18d.
- b. VISIA 7 will be done by trained technician for T18d.
- c. OCT scan will be done by trained technician for T18d.
- d. Corneometer will be done by trained technician for T18d.
- e. Vapometer will be done by trained technician for T18d.
- f. Cutometer will be done by trained technician for T18d.
- g. pH meter will be done by trained technician for T18d.
- h. Self-assessment questionnaire will be answered by subjects for T18d.
- i. Adverse Events/Local Intolerance will be checked and recorded.

Evaluation visit on T22d (7-day after self-recovery)

- a. Clinical Assessment will be done by dermatologist for T22d.
- b. VISIA 7 will be done by trained technician for T22d.
- c. OCT scan will be done by trained technician for T22d.
- d. Corneometer will be done by trained technician for T22d.
- e. Vapometer will be done by trained technician for T22d.
- f. Cutometer will be done by trained technician for T22d.
- g. pH meter will be done by trained technician for T22d.
- h. Self-assessment questionnaire will be answered by subjects for T22d.
- i. Adverse Events/Local Intolerance will be checked and recorded.

Evaluation visit on T25d (10-day after self-recovery and post-treatment started)

- a. Subjects wash face with usual cleanser, then pat dry with clean tissue paper at center.
- b. Acclimatization to the room condition for 30 minutes (the conditions with a well-controlled room temperature $(21\pm1 \, ^{\circ}\text{C})$ and humidity $(45\%\pm5 \, \%)$.
- c. Clinical Assessment will be done by dermatologist for T25d.
- d. VISIA 7 will be done by trained technician for T25d.
- e. OCT scan will be done by trained technician for T25d.
- f. Corneometer will be done by trained technician for T25d.
- g. Vapometer will be done by trained technician for T25d.
- h. Cutometer will be done by trained technician for T25d.
- i. pH meter will be done by trained technician for T25d.
- j. LA sting test will be done by trained technician for T25d.
- k. Self-assessment questionnaire will be answered by subjects for T25d.
- 1. The investigational products and standard products will be weighted and returned to subjects, meanwhile, the daily log will be also checked.
- m. Adverse Events/Local Intolerance will be checked and recorded.

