Subjects will be pushed and required to answer one on-line questionnaire after the first application of test product at home.

Evaluation visit on T32d (7-day post-treatment started)

- a. Subjects wash face with usual cleanser, then pat dry with clean tissue paper at center.
- b. Acclimatization to the room condition for 30 minutes (the conditions with a well-controlled room temperature $(21\pm 1 \, ^{\circ}\text{C})$ and humidity $(45\% \pm 5 \, \%)$.
- c. Clinical Assessment will be done by dermatologist for T32d.
- d. VISIA 7 will be done by trained technician for T32d.
- e. OCT scan will be done by trained technician for T32d.
- f. Corneometer will be done by trained technician for T32d.
- g. Vapometer will be done by trained technician for T32d.
- h. Cutometer will be done by trained technician for T32d.
- i. pH meter will be done by trained technician for T32d.
- j. Self-assessment questionnaire will be answered by subjects for T32d.
- k. The investigational products and standard products will be weighted and returned to subjects, meanwhile, the daily log will be also checked.
- 1. Adverse Events/Local Intolerance will be checked and recorded.

Evaluation visit on T39d (14-day post-treatment started)

- a. Subjects wash face with usual cleanser, then pat dry with clean tissue paper at center.
- b. Acclimatization to the room condition for 30 minutes (the conditions with a well-controlled room temperature $(21\pm 1 \, ^{\circ}\text{C})$ and humidity $(45\% \pm 5 \, \%)$.
- c. Clinical Assessment will be done by dermatologist for T39d.
- d. VISIA 7 will be done by trained technician for T39d.
- e. OCT scan will be done by trained technician for T39d.
- f. Corneometer will be done by trained technician for T39d.
- g. Vapometer will be done by trained technician for T39d.
- h. Cutometer will be done by trained technician for T39d.
- i. pH meter will be done by trained technician for T39d.
- j. LA sting test will be done by trained technician for T39d.
- k. Self-assessment questionnaire will be answered by subjects for T39d.
- The investigational products and standard products will be weighted and returned; meanwhile, the daily log will be also checked.
- m. Adverse Events/Local Intolerance will be checked and recorded.

NB: all concomitant medications, AEs and local intolerances will be reported throughout the study.

8. Biostatistics and Data Management

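### At T14d, T25d and T39d the lactic acid stinging test is listed directly before the self-assessment questionnaire, so provoked sensations can carry over into comfort-type answers

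*Protocol*

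**What the plan says.** Section 7.2 of the Protocol sets out each visit as a lettered list. At T14d, step j is "LA sting test will be done by trained technician for T14d" and step k is "Self-assessment questionnaire will be answered by subjects for T14d". At T25d the same two steps are "LA sting test will be done by trained technician for T25d" and "Self-assessment questionnaire will be answered by subjects for T25d". At T39d step j is "LA sting test will be done by trained technician for T39d", and the questionnaire is again step k.

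T32d has no lactic acid test. There the questionnaire, "Self-assessment questionnaire will be answered by subjects for T32d", comes directly after "pH meter will be done by trained technician for T32d". The T16d, T18d and T22d lists also go from the pH meter to the questionnaire. The study schedule table in section 4 agrees: lactic acid test at T0, T14d, T25d and T39d only.

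Section 5.2 describes the test as 10% lactic acid scored against distilled water. Its self-report covers "intensity of symptoms (stinging, itchiness, burning and other) will be answered by subject at 30 seconds, 2.5 minutes, 5 minutes after lactic application". Neither section gives a waiting time, a rinse or an instruction to set the test aside when answering the next form.

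Section 5.6 gives the efficacy questionnaire to Group 1 at T14d, T25d, T32d and T39d; the cosmeticity questionnaire to Group 1 at T14d and T39d; and the post-procedure tolerance questionnaire to all groups at T15d, T16d, T18d, T22d and T25d.

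**The concern.** The lactic acid test is a deliberate irritant challenge. It has the woman score unpleasant skin sensations several times over five minutes. The next listed step asks her to rate her skin, with items on comfort and, at some visits, on redness and discomfort. Even if the physical reaction has faded, she has just been made to attend to those sensations. Clinical grading, imaging and instruments are all listed before the challenge and so are shielded from it. The self-report is not.

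Two things are at stake. One is the level of the Group 1 share of ratings 4 or 5, which section 8.3.1 says will be reported. The other is comparison over time, because some visits in a series carry the challenge and others do not. Later analysis cannot separate an order effect from a product effect.

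**Working it through.** No formula applies; the check sets the visit lists, section 5.6 and Annex 11.3 side by side. Annex 11.3 does not say which of its three item sets belongs to which questionnaire in section 5.6. The item sets below are matched to visits by the days in the annex headings, which is my reading.

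| Visit | Lactic acid test | Step listed before the questionnaire | Item set (Annex 11.3) | Questionnaires (5.6) |
|---|---|---|---|---|
| T14d | yes | lactic acid test | pre-treatment | efficacy, cosmeticity |
| T15d | no | face wash | none matched | tolerance |
| T16d, T18d, T22d | no | pH meter | recovery | tolerance |
| T25d | yes | lactic acid test | recovery | efficacy, tolerance |
| T32d | no | pH meter | post-treatment | efficacy |
| T39d | yes | lactic acid test | post-treatment | efficacy, cosmeticity |

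**Visits that follow a challenge**
- Efficacy: T14d, T25d, T39d = 3 of 4.
- Cosmeticity: T14d, T39d = 2 of 2.
- Tolerance: T25d = 1 of 5.

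**Items that ask directly about comfort, redness or discomfort (my count from Annex 11.3)**
- Pre-treatment set: comfort and redness, 2 of 14. A further item on comfort for the procedure is less direct.
- Recovery set: comfort, redness, and discomfort such as redness, dryness or itch, 3 of 8. The same less direct item appears here too.
- Post-treatment set: comfort only, 1 of 12. There is no redness item.

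Comfort-type items are therefore exposed at all three visits; redness or discomfort items only at T14d and T25d.

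**Where the condition changes within a series**
- Recovery: T16d, T18d and T22d unchallenged, T25d challenged.
- Post-treatment: T32d unchallenged, T39d challenged.
- The pre-treatment set is used once, so only its level can be affected. Both cosmeticity visits are challenged, so they are consistent with each other and again only the level is at risk.

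**Size.** The Protocol gives nothing from which to estimate it. As a scale only: with 30 Group 1 completers, each woman who moves from 4 to 3 on an item changes the share of ratings 4 or 5 by 1/30 = 3.3 percentage points. If, as a pure assumption, 3 to 6 women did so, the share would fall by 3/30 = 10 to 6/30 = 20 points.

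**The case against.** The strongest reply is that carry-over is not shown. Section 5.2 gives neither the application site nor how long symptoms last beyond the five-minute scoring. Section 7.2 gives no clock times and does not say that its letters bind the order. Most items concern product effect, appearance or willingness to recommend, not sensation at that moment. All of this stands, and it limits the point to a risk for a small set of items. The lists do, however, read as a sequence: washing and acclimatisation come before measurement, and at T15d the laser comes before the post-procedure assessments.

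A reader might infer several stronger things that the Protocol does not support:
- *That comfort, redness and tolerance results are all contaminated at all three visits.* The tolerance questionnaire meets the challenge only at T25d, and redness is not asked in the post-treatment set.
- *That the group comparison is biased.* Both arms have the test at the same visits. A serum effect on stinging could still make carry-over differ between arms at T25d, but the schedule does not create that. The tolerance feedback compared between groups in section 8.3.2 has the fields of the home diary in Annex 11.4, which the order of clinic steps does not touch.
- *That a product claim is inflated.* Carry-over of discomfort would more likely lower Group 1 ratings.
- *That key endpoints are affected.* The Protocol names none, and the questionnaire paragraph in section 8.3.1 specifies no test between visits.

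**Conclusion.** The ordering defect is real and its consequence is modest. Provoked sensations can carry over into comfort-type answers at T14d, T25d and T39d, and into redness or discomfort answers at T14d and T25d. The clearest harm is to reading change over time, because the challenge appears only at the last visit of the recovery series (T25d against T16d to T22d, including the tolerance questionnaire) and of the post-treatment series (T39d against T32d). For the efficacy questionnaire there is no control arm in which a shift could be seen.

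The size is unknown; the scale shown above is not an estimate. The conclusion assumes that the lettered steps are carried out in order and that no unstated pause or instruction intervenes. It does not touch the instruments, the clinical grading, the sample size or the significance level.

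**What to change.** In section 7.2, at T14d, T25d and T39d, swap steps j and k so that the self-assessment questionnaire is completed before the lactic acid test. The test then comes last among the assessments, as it already does at T0, and no questionnaire at these visits follows a challenge. The closing adverse event and local intolerance check can stay last, where it also picks up reactions to the test itself.

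The cost is two lines exchanged in three visit lists, with no added procedure, time or data. If visits have already been run in the listed order, the report should state that order beside the questionnaire percentages. It should not attribute a change from T32d to T39d, or from T22d to T25d, on comfort-type items to the product alone.
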